13.4.2. Part 2: Expansion Cohort

The sample size and stopping rules are based on the methodology of Lee et al. [Lee, 2008]. The predictive probability design is similar to a Green-Dahlberg design in that it allows for early stopping for futility. The differences are that the predictive probability design allows for evaluation of stopping rules after each subject, rather than at only two stages, once a minimum number of subjects are evaluable. In this particular study, we will stop only for futility.

Bayesian statistics will be employed to calculate the predictive probability that the response rate is greater than the historic response rate at interim analyses using a weak/non-informative prior. A Bayesian analysis expresses uncertainty about a parameter in terms of probability. A prior distribution is defined to characterize the level of knowledge about a parameter before the data are collected. Once the data are collected, a posterior distribution is formed using the prior distribution and the observed data. A very weak prior Beta distribution with a mean response rate equal to the target response rate is assumed. Thus, the posterior distribution for the response rate will be primarily driven by the data and can be derived as follows:

Let p denote the response rate, the number of responses in the current n subjects, x , follows a binomial distribution, Binomial (n , p). Taking the Bayesian method and combining the prior distribution and the observed data x , the posterior distribution of the response rate follows a beta distribution, i.e.

In the following case, 30% is the target response rate.

$$p \sim \text{Beta} (0.03 + x, 0.07 + n-x) \text{ with the posterior mean } (0.03+ x)/(0.07 + n).$$

For each cohort, to test hypotheses:

$$H_0: RR \leq 10\%$$

$$H_A: RR \geq 30\%$$

When maximum sample size is 30, the design will have a Type I error (α) of 0.064 and 89% power with the probability of early termination is 0.88 when the treatment is futile and probability of early termination 0.084 when the treatment is effective (true RR=0.3). Futility analysis for each dose expansion cohort will begin when response data is available for at least 10 evaluable subjects. The dose expansion cohort may be stopped early for futility if the predictive probability of success (response rate \geq historical response rate) is less than 5%. Futility stopping rules are described below.

After 10 evaluable subjects have been enrolled to examine safety and efficacy, the number of observed objective responses will guide further enrolment according to the rules summarized in [Figure 3](#). A maximum of **30** subjects will be enrolled at the RP2Ds for GSK2879552 and GSK2879552 2 in combination with ATRA, respectively. All available data will be considered in making enrollment decisions. If both cohorts enroll the maximum number of subjects, this will result in 60 subjects total. Data from part 1 may be combined with data from part 2 in the analysis to achieve the above final and interim analysis sample sizes.

Figure 3 Diagram of Stopping Rules for Cohort Expansion: GSK2879552

Number of Subjects	Number of Responses						
	0	1	2	3	4	5	≥ 6
10	Shaded						
11	Shaded						
12	Shaded						
13	Shaded						
14	Shaded						
15	Shaded	Shaded					
16	Shaded	Shaded					
17	Shaded	Shaded					
18	Shaded	Shaded					
19	Shaded	Shaded					
20	Shaded	Shaded					
21	Shaded	Shaded	Shaded				
22	Shaded	Shaded	Shaded				
23	Shaded	Shaded	Shaded				
24	Shaded	Shaded	Shaded				
25	Shaded	Shaded	Shaded	Shaded			
26	Shaded	Shaded	Shaded	Shaded			
27	Shaded	Shaded	Shaded	Shaded			
28	Shaded	Shaded	Shaded	Shaded	Shaded		
29	Shaded	Shaded	Shaded	Shaded	Shaded		
30	Shaded	Shaded	Shaded	Shaded	Shaded	Shaded	

The shaded regions are the specific regions for stopping the study for futility. For instance, if there is only one response in fifteen subjects, then the predictive probability for success will be 5.0% or less (the futility criterion) and the study will be stopped.

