- No subjects treated at next higher dose level have toxicity meeting the above criteria.

However, the dose escalation may continue with multiple subjects per cohort per the clinical judgment of the Medical Monitor and internal dose-escalation committee in consultation with the investigators. The decision on the number of subjects will be documented in writing together with the dose escalation decision and the rationale.

Maximum Dose Increment

Built-in safety constraints are in place to prevent exposing subjects to undue risk of toxicity. The dose increment will be no more than 100% of the current dose in the absence of any safety signals. The dose increment will be no more than 50% of the current dose after DLT or any Grade 2 or higher non-hematologic adverse event that is considered related to the study medication (with the exceptions as above) is observed. The maximum allowable dose increment will be determined based on the prior dose level data.

Completion of Dose Escalation

The dose escalation will complete when MTD and/or RP2D is determined. The RP2D will be the MTD or a lower dose that provides adequate PK exposure and biologic activity with superior tolerability. The identification of MTD may not be necessary if a clear RP2D emerges without reaching the MTD. The final determination of RP2D will be based on the N-CRM suggested dose level, or the biologically active dose (e.g., clinical response), the safety profile, and available PK and PD data generated from all subjects in Part 1. Up to 12 additional subjects will be enrolled at the dose to further define the safety and tolerability of the dose and schedule. If necessary, alternate schedules can be explored to determine additional biologically active doses even after a RP2D is defined.

Dose Escalation Committee

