4.2.6. Maximum Tolerated Dose and Recommended Phase 2 Dose

The MTD is defined as the dose with the highest posterior probability of subjects experiencing a DLT in the first 28 days on treatment in the target interval [16%,33%], and for which the probability that the DLT rate lies within the excessive toxicity or the unacceptable toxicity windows is less than 25%. The interval boundaries of 16% and 33% are chosen to be consistent with the traditional 3+3 design toxicity boundary which is 1/6 and 1/3.

The RP2D will be MTD or a lower dose that provides adequate PK exposure and biologic activity with superior tolerability. Up to 12 additional subjects will be enrolled at the dose to further define the safety and tolerability of the dose and schedule. The RP2D may be different for mono-therapy and for the combination therapy with ATRA.

Data considered for RP2D selection will include, but not be limited to: safety, available PK profile, and observed signs of clinical activity from Part 1.

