13.7.2. Part 2: Expansion Cohort

After the initial 10 evaluable subjects have enrolled at the RP2D dose, response data will be reviewed on an ongoing basis and the number of responses observed will be compared

with the stopping rules provided in Section 13.4.2. As noted in Section 13.4 data from Part 1 at the RP2D may be combined with data from part 2 to achieve the required number of subjects for the response rate analysis.

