13.8.1. Anti-Cancer Activity Analyses

For Part 1, anti-tumor activities will be evaluated based on clinical evidence and response criteria. If the data warrant, the response data will be summarized by dose level.

The primary aim of Part 2 is to detect a clinically meaningful response rate of 30% relative to a 10% response rate suggesting no activity.

Response rate (RR) is defined as the percentage of subjects who achieved CR, CRp, PR or morphologic leukemia-free state (MLFS) among subjects who received at least one dose of treatment. Response rate and the associated 2-sided 95% exact confidence limits will be provided. A waterfall plot of percent change from baseline in bone marrow blasts and peripheral blasts will be provided.

As a secondary analysis, if data warrant, PFS, OS, DOR, and TTR will be evaluated using the Kaplan-Meier method. Summaries of median time to event, quartiles and 95% CIs will be presented.

For the analysis of PFS, if the subject received subsequent anti-cancer therapy prior to the date of documented events, PFS will be censored at the last adequate assessment (e.g. assessment where visit level response is CR, CRp, PR, MLFS, or SD) prior to the

initiation of therapy. Otherwise, if the subject does not have a documented date of events, PFS will be censored at the date of the last adequate assessment. For the analysis of overall survival (OS), the last date of known contact will be used for those subjects who have not died at the time of analysis; such subjects will be considered censored. Further details on rules for censoring will be provided in the RAP. Sensitivity analyses of PFS and further details on censoring rules will be provided in the RAP. Progression free survival (PFS) and overall survival (OS) will be summarized using Kaplan-Meier method.

The duration of response is defined for the subject or subjects with a CR, CRp, MLFS, or PR, as the time from the first documented evidence of a CR, CRp, MLFS, or PR until the first documented disease progression or death due to any cause. Censoring rules for duration of response will be outlined in detail in the RAP.

Time to Response is defined, for subjects with a CR, CRp, MLFS, or PR, as the time from first dose to the first documented evidence of responses (PR or better).

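### The stated Part 2 type I error of 0.064 does not cover the permitted design, in which Part 1 subjects at a dose chosen partly on response may be counted in the test

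*Protocol*

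**What the plan says.** Protocol 13.4.2 tests a null response rate of at most 10% against 30% in each expansion cohort. It applies the Figure 3 futility boundary from the tenth evaluable subject onward. "When maximum sample size is 30", it states, "the design will have a Type I error (α) of 0.064 and 89% power". The same section then adds: "Data from part 1 may be combined with data from part 2 in the analysis", for the purpose of reaching the interim and final sample sizes. Section 13.7.2 narrows this to subjects at the selected dose: "data from Part 1 at the RP2D may be combined with data from part 2".

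Two sections describe how that dose is selected. Section 4.2.1 bases the final choice on the N-CRM dose "or the biologically active dose (e.g., clinical response"), together with safety, PK and PD. Section 4.2.6 lists "observed signs of clinical activity from Part 1" among the data considered.

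Section 13.8 foresees separate Part I and Part II analyses where applicable, and combined data for some end-of-trial analyses at the same dose. No section says that a Part 2-only test is primary, fixes in advance whether or how many Part 1 subjects are pooled, or recalculates the error rate for pooled data. SAP 2.1 records that Part 2 was not initiated and will not be analysed.

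**The concern.** If a dose goes forward partly because its Part 1 subjects responded, those subjects' response count is no longer an ordinary binomial draw at the true rate. It is tilted upward. Counting them among the 30 carries that tilt into the test. The word 'may' opens a second route: in an open-label study, whether to pool can be decided once the Part 1 responses at the RP2D are known.

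At stake is the chance of declaring activity for a regimen whose true rate is 10%, which 13.8.1 describes as "relative to a 10% response rate suggesting no activity". The response estimate would also be too high. A reader of 13.4.2 would take 0.064 as a property of the design the protocol permits, and it is not.

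**Working it through.** **Inputs.** Null rate 10%, alternative 30%, maximum 30 (13.4.2). Figure 3 stops at 0 responses for n = 10-14, at most 1 for 15-20, 2 for 21-24, 3 for 25-27 and 4 for 28-29; success is 6 or more of 30. Part 1 numbers per dose: 1 per monotherapy cohort until a toxicity trigger, then at least 2 (4.2.1); 3 or more per combination cohort (4.2.2); up to 12 with expansion (4.2.3).

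**Step 1: the plan's own figures.** Let f(n, x) be the probability that the cohort is still open with x responses after n subjects. Then f(n, x) = (1 − p)·f(n−1, x) + p·f(n−1, x−1), with f set to 0 wherever x is at or below the boundary for n = 10-29. Success is the sum of f(30, x) over x ≥ 6.
- p = 0.10: success 0.0637, early termination 0.8816 (stated 0.064 and 0.88).
- p = 0.30: success 0.8913, early termination 0.0838 (stated 89% and 0.084).

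All four figures reproduce for 30 new, unselected subjects.

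**Step 2: pooling alone.** Let the first m subjects come from Part 1, with the dose chosen without regard to response and pooling fixed in advance. Alpha is 0.0637 for m = 3 to 10 and 0.0651 for m = 12. The slight rise occurs because the looks at 10 and 11 are skipped.

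**Step 3: selection on response.** K doses have m subjects each, all with a true rate of 10%, and the dose with the most responses is carried forward. Its count M satisfies P(M ≤ x) = F(x)^K, where F is the Binomial(m, 0.10) distribution function. The recursion then starts at n = m from that distribution.

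Example, m = 3 and K = 2: F = 0.729, 0.972, 0.999, 1. Squaring and differencing gives P(M = 0, 1, 2, 3) = 0.5314, 0.4133, 0.0532, 0.0020. The chance of success from each start is 0.0369, 0.1185, 0.2772, 0.5128. Alpha = 0.0196 + 0.0490 + 0.0148 + 0.0010 = 0.0844.

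The last column averages each result with its unselected value, as if response decided the dose half the time.

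| m per dose | K = 2 | K = 3 | K = 4 | Half weight, K = 2 to 4 |
|---|---|---|---|---|
| 1 | 0.0724 | 0.0803 | 0.0873 | 0.0680-0.0755 |
| 2 | 0.0791 | 0.0918 | 0.1025 | 0.0714-0.0831 |
| 3 | 0.0844 | 0.1006 | 0.1134 | 0.0740-0.0886 |
| 6 | 0.0957 | 0.1192 | 0.1376 | 0.0797-0.1006 |
| 12 | 0.1105 | 0.1457 | 0.1747 | 0.0878-0.1199 |

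**Step 4: optional pooling alone.** There is no dose selection on response; Part 1 is pooled only if its rate exceeds 10%, and otherwise 30 new subjects are used. Alpha = P(favourable) × P(success given favourable) + P(unfavourable) × 0.0637.
- m = 3: 0.271 × 0.1358 + 0.729 × 0.0637 = 0.083
- m = 6: 0.4686 × 0.1167 + 0.5314 × 0.0637 = 0.088
- m = 12: 0.341 × 0.1721 + 0.659 × 0.0637 = 0.101

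**Step 5: the estimate.** With m = 12, the mean of M is 1.756 for K = 2 and 2.298 for K = 4. Ignoring early stopping, the expected pooled rate is (1.756 + 18 × 0.10)/30 = 11.9% and (2.298 + 1.8)/30 = 13.7%, against a true 10%.

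**The case against.** The strongest reply is that the larger figures are unrealistic, and much of it stands. Response is one listed input beside the N-CRM dose, safety, PK and PD, so letting it alone choose the dose is an upper bound. Monotherapy escalation can run at 1 or 2 subjects per dose, where even the upper scenario is 0.072-0.103. Twelve subjects at each of 4 doses is 48 in one arm, whereas 3.1 plans about 55 escalation and 25 PK/PD expansion subjects over both arms. Sections 4.2.1 and 4.2.6 also provide up to 12 additional subjects at the chosen dose. If they enrol after the choice is made, their responses did not select it, and pooling them under a rule fixed in advance adds no bias.

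Section 13.8 already foresees separate analyses by part. That narrows the criticism without answering it: 13.4.2 and 13.7.2 apply pooling to the sample sizes for the decision itself, and nothing makes the Part 2-only test primary.

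Three stronger readings are tempting, and the documents do not support them. One is that pooling as such inflates the error; step 2 shows it does not. Another is that only Part 1 responders are carried over; 13.7.2 refers to Part 1 data at the RP2D, without restriction to responders. The third is that a trial result is biased; SAP 2.1 shows the test was never run. The opposite reading, that 0.064 is safe whenever response plays no part in choosing the dose, also fails, because optional pooling alone raises it (step 4).

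**Conclusion.** The point holds as a design flaw. The stated 0.064 is correct for 30 subjects whose responses influenced neither the dose choice nor the decision to pool, and the protocol permits a design that does not meet that condition. In the settings examined, the direction is upward whenever response affects either choice.

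The size is not determined by the documents. The number of doses compared, the number of subjects pooled and the weight given to response are all assumptions here. Across 2 to 4 doses and 1 to 12 subjects per dose, alpha is 0.072-0.175 if response alone decides and 0.068-0.120 if it decides half the time. Optional pooling gives 0.083-0.101 for 3 to 12 pooled subjects. The value 0.175 should not be read as the design's error rate; it is the far corner of the upper scenario. With Part 2 unopened, the practical consequence is for any later expansion that reuses this rule.

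**What to change.** State in 13.4.2 and 13.7.2 that the Figure 3 looks and the 6-of-30 decision use only subjects enrolled in Part 2, and that the pooled Part 1 + Part 2 rate is supportive. This aligns both sections with the separate analyses foreseen in 13.8 and restores alpha 0.0637 and power 0.891.

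Alternatively, keep pooling but fix before any Part 1 response is known whether and which Part 1 subjects count. Then restate alpha and power from simulations that include the dose-selection step.

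The first option is a wording change and stays within the 30 per cohort (60 in total) already planned. It is not free: it gives up the saving of up to about 12 subjects per cohort that pooling would allow, and the first futility look must wait for 10 new evaluable subjects. The second option keeps some of that saving at the cost of a simulation exercise, and possibly a stricter success boundary.

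### Figure 3 and the quoted Part 2 error rates do not follow from the stated Beta(0.03, 0.07) prior and 5% futility rule: three cells that meet the rule are left unshaded

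*Protocol*

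**What the plan says.** All of this is in Protocol Section 13.4.2 unless noted.

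- **Hypotheses.** The aim is to detect a response rate of "30% relative to a 10% response rate suggesting no activity" (Section 13.8.1).
- **Prior.** "A very weak prior Beta distribution with a mean response rate equal to the target response rate is assumed". The posterior is printed as Beta(0.03 + x, 0.07 + n − x), so the prior is Beta(0.03, 0.07), with mean 0.03/0.10 = 0.30. The posterior mean is printed with denominator 0.07 + n.
- **Looks.** "Futility analysis for each dose expansion cohort will begin when response data is available for at least 10 evaluable subjects". The rule is then applied after every subject.
- **Cut-off.** The text uses a predictive probability under 5%. The note to Figure 3 applies it to 1 response in 15: "then the predictive probability for success will be 5.0% or less (the futility criterion) and the study will be stopped".
- **Figure 3.** "The shaded regions are the specific regions for stopping the study for futility". Shading covers 0 responses at n = 10–14, up to 1 at 15–20, up to 2 at 21–24, up to 3 at 25–27, up to 4 at 28–29, and up to 5 at n = 30.
- **Operating characteristics.** "When maximum sample size is 30, the design will have a Type I error" "of 0.064 and 89% power with the probability of early termination is 0.88 when the treatment is futile", with "probability of early termination 0.084 when the treatment is effective (true RR=0.3").

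The posterior probability that would count as success at n = 30 is not given. SAP Section 2.1 records that Part 2 was not started before the study closed.

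**The concern.** In a predictive-probability design, the prior, the success criterion at the maximum sample size and the futility cut-off together fix every cell of the stopping table. The table then fixes the error rates. A reader should therefore be able to start from Beta(0.03, 0.07) and 5% and arrive at Figure 3 and the four quoted figures. That does not happen.

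The conflict sits on the decision boundary. At three combinations of subjects and responses the written criterion is met while the figure indicates continued enrolment. These are not rare outcomes in an inactive cohort. Following Figure 3, a cohort with a true response rate of 10% passes through at least one of the three cells with probability 0.48 (0.25 for 1/14 alone). The probability is 0.24 at a true rate of 20% and 0.05 at 30%. Two such cohorts were planned.

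**Working it through.** **1. Reproduce the plan's own figures.** Inputs: the Figure 3 boundaries listed above, looks at n = 10 to 29, and success at 6 or more of 30. An exact binomial recursion adds one subject at a time and removes the probability that falls in a shaded cell.

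| | Quoted | Figure 3 as drawn |
|---|---|---|
| Type I error (RR 10%) | 0.064 | 0.0637 |
| Power (RR 30%) | 89% | 0.8913 |
| Early termination, RR 10% | 0.88 | 0.8816 |
| Early termination, RR 30% | 0.084 | 0.0838 |

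All four agree, so the shading has been read correctly and the quoted rates are those of the figure.

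**2. Success criterion.** Row 30 shades 0 to 5, which makes success 6 or more. The stated type I error supports this: with success at 5 or more under the stated prior and 5% rule, it would be 0.146 rather than 0.064. This is an inference, not a statement in the protocol.

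**3. Apply the stated prior and cut-off.** With x responses in n subjects, the number of further responses Y among the remaining 30 − n is Beta-Binomial(30 − n, 0.03 + x, 0.07 + n − x), and

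PP(n, x) = P(Y ≥ 6 − x).

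- 1/14: Y ~ Beta-Binomial(16, 1.03, 13.07); P(Y ≥ 5) = 0.0381
- 2/20: Y ~ Beta-Binomial(10, 2.03, 18.07); P(Y ≥ 4) = 0.0364
- 3/24: Y ~ Beta-Binomial(6, 3.03, 21.07); P(Y ≥ 3) = 0.0461

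Numerical integration of the binomial tail over the posterior gives the same values. None is close enough to 5% for the difference between under 5% and 5% or less to matter. The cells on either side agree with the figure:

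| Responses | One subject earlier (unshaded) | Disputed cell (unshaded) | One subject later (shaded) |
|---|---|---|---|
| 1 | 1/13: 0.0539 | 1/14: 0.0381 | 1/15: 0.0262 |
| 2 | 2/19: 0.0548 | 2/20: 0.0364 | 2/21: 0.0227 |
| 3 | 3/23: 0.0755 | 3/24: 0.0461 | 3/25: 0.0245 |

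Every other cell matches. Each mismatch is one subject wide.

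**4. Operating characteristics of the stated rule.** Shading the three cells and repeating step 1:

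| | Figure 3 as drawn | Stated prior and 5% | Difference |
|---|---|---|---|
| Type I error | 0.0637 | 0.0612 | −0.0025 |
| Power | 0.8913 | 0.8821 | −0.0092 |
| Early termination, RR 10% | 0.8816 | 0.8888 | +0.0072 |
| Early termination, RR 30% | 0.0838 | 0.0952 | +0.0114 |
| Expected n, RR 10% | 17.79 | 16.99 | −0.80 |

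**5. What would generate Figure 3?** Each of these reproduces every cell:

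- the stated Beta(0.03, 0.07) with a cut-off between about 2.7% and 3.6%;
- a prior with mean 0.30 and a + b of about 2.2 to 2.45 at 5%, for example Beta(0.69, 1.61);
- Beta(0.5, 0.5) at 5%.

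Beta(0.3, 0.7) at 5% does not, because it stops at 2/20 (0.0423).

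**6. Posterior mean.** For Beta(0.03 + x, 0.07 + n − x) the parameters sum to 0.10 + n, so the mean is (0.03 + x)/(0.10 + n). The printed denominator, 0.07 + n, would imply a Beta(0.03, 0.04) prior. That reading leaves the same three mismatches (0.0383, 0.0365, 0.0462).

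**The case against.** **The rule is not binding.** The cut-off sentence in Section 13.4.2 is permissive, and Sections 4.3 and 13.4.2 leave enrolment decisions to all the available data. The firm wording is attached to 1/15, where text and figure agree. This stands as a limit on consequences: the text does not compel a stop at 1/14, 2/20 or 3/24. It does not remove the inconsistency, because whether a cell meets a 5% criterion is a calculation and Figure 3 is presented as its result.

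**The figure is the operative rule.** Section 13.4.2 sends enrolment decisions to Figure 3, and a team that follows it obtains the quoted error rates. This also stands. The quoted figures are correct for the figure; what fails is the stated route to it.

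**Success at 6 of 30 is inferred.** True, and the finding depends on it. With 5 of 30 the three cells would not be stops under the stated prior and 5% rule, but that contradicts row 30 and raises the type I error to 0.146.

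**The effect is small and Part 2 never opened.** Both are correct.

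**A stronger reading to avoid.** Because Beta(0.5, 0.5) at 5% reproduces the whole of Figure 3, a reader might infer that the quoted error rates come from a different prior, and from that one in particular. The documents do not support this. A cut-off near 3% with the stated prior fits equally well, as does another prior with mean 0.30, so the sentence about the prior mean need not be the mistake.

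**Conclusion.** Figure 3 and the four quoted operating characteristics agree with each other, but they do not follow from the stated Beta(0.03, 0.07) prior and 5% cut-off. The written rule places 1/14, 2/20 and 3/24 in the stopping region and the figure does not. The conclusion rests on success being 6 or more of 30.

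The documents do not identify which of the prior, the cut-off or the shading is wrong. It would also be too strong to say that the design's error rates are misstated: they are right for the boundary as drawn. Power and early-termination probabilities move by about one percentage point and type I error by about a quarter of a point. No decision in this study was affected, because Part 2 was not initiated. It is a modest but checkable error in a pre-specified boundary, and worth correcting if the design text is reissued or reused.

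**What to change.** Reconcile the prior, the cut-off and Figure 3 in Section 13.4.2, in one of two ways:

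1. Keep Beta(0.03, 0.07) and 5%. Shade 1/14, 2/20 and 3/24, and restate type I error 0.061, power 88%, and early termination 0.89 (RR 10%) and 0.095 (RR 30%).
2. Keep Figure 3 and the quoted figures, and state the prior and cut-off that actually generated them. The design team's simulation or software record should settle which these were; they should not be chosen by fitting.

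In either case, write the success criterion down (at least 6 responses in 30, with the posterior threshold behind it), correct the posterior-mean denominator to 0.10 + n, and use one form of the cut-off in the text and in the note to the figure.

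The first route costs three cells and four numbers; the second costs about one sentence. Neither changes the sample size or the data collected.
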